#### 6.5. Software for simulation and analysis

Study design, simulations, interim analysis and final analysis of primary outcome will be carried out by ICON ADDPLAN V 6.1. This is a proprietary statistical package that contains approved algorithm for dealing with the adaptive design according to EMA and FDA standards. The analysis of secondary outcomes will be carried out at the end of the trial and will be carried out by STATA V.15.

**Figure 2 Adaptive sample size and power.** The yellow bars represent the number of patients to be enrolled in the trial. Red dotted line shows the study power (i.e. the probability to detect a real difference between arm 1 and arm 2 if arm 1 is superior to arm 2 is). Simulation has been carried out assuming 1:1 ratio between arms; first analysis is carried out at 200 patients; adaptive sample size between 30-350 and p-value calculated according Fisher exact statistics conditional power for next analysis 90%; K=3 (i.e. 2 interim analysis and one final analysis).

**Figure 3 Cumulative probability of trial termination.** Continuous lines show the cumulative probability of **early termination** either at first (green line) or second (yellow line) interim analysis. Early termination at both stages can be driven either by efficacy (i.e. reject H0) or futility (i.e. accept H0). The red dotted line shows the cumulative probability to **termination for futility** regardless the stage of analysis (i.e. at first interim, second interim or final analysis).

## 7. Safety measurements

### 7.1. Definitions

An adverse event is defined in the International Conference on Harmonization (ICH) Guideline for Good Clinical Practice as “any untoward medical occurrence in a patient or clinical investigation subject administered a pharmaceutical product and that does not necessarily have a causal relationship with this treatment.”

Events will be reviewed and classified by the site PI. The relationship of the event to the study drug and whether the event is an expected event or not will be assessed using the listing of adverse effects contained in the summary of product characteristics for the glucocorticoid drugs used.

The treating team has the primary responsibility for reviewing laboratory test results and determining whether an abnormal value in an individual study participant requires action. In general, abnormal laboratory without clinical significance (based on clinical judgment) should not be recorded as adverse events; however, laboratory value changes requiring therapy or adjustment in prior therapy are considered adverse. The investigators should liaise closely with the treating teams and remain aware of any such adverse events.

Serious adverse event (SAE) are defined as an adverse event that:

- Is fatal
- Is life threatening (places the participant at immediate risk of death)
- Requires in-patient hospitalization or prolongation of existing hospitalization
- Results in persistent or significant disability/incapacity
- Causes a congenital anomaly/birth defect
- Other significant medical hazard

However, since both the study drugs have been in wide clinical use for many years, their effects and possible adverse events are well recognized. As such, although adverse events may occur, we would not anticipate that they would be unexpected or widely divergent from established frequencies. Rarely, life threatening adverse reactions can occur with the use of any glucocorticoid. Other serious adverse events might include hyperglycemia, psychosis, depression or other psychic disorder, increased liver enzymes, venous thrombosis, wound healing impairment. However, multiple meta-analyses, involving thousands of critically ill patients with sepsis or ARDS, have demonstrated a relatively low-dose and short treatment courses like the ones proposed in this study are rarely associated with serious complications.(13)

All deaths and SAEs will be notified to the local PI and site research governance, along with the DSMB, who will then notify the Italian Regulatory Agency (AIFA). Unforeseen adverse events will be discussed with collaborating investigators at other Centers; such information will be regularly reviewed. If any member of the trial team becomes aware of an unexpected death or serious adverse

event at any stage of the trial review period, the PI will be alerted. All deaths and adverse events will be recorded and reported in the final analysis.

## 7.2. Collecting, Recording and Reporting of “Serious Adverse Event (SAE)/Safety/Suspected Unexpected Serious Adverse Reaction (SUSAR)”

Any events that are unexpected (in terms of severity or frequency), that can reasonably be attributed to the drug under study and that may expose other subjects to harm will be reported. SAE/Safety/SUSAR events refers to problems, in general, to include any incident, experience, or outcome (including adverse events) that meets ALL of the following criteria:

1. Unexpected

In terms of nature, severity or frequency of the problem as described in the study documentation (e.g., protocol, consent documents etc.);

2. Related or possibly related to participation in the research

Possibly related means there is a reasonable possibility that the problem may have been caused by the procedures involved in the research;

3. Risk of harm

Suggests that the research places participants or others at a greater risk of harm (including physical, psychological, economic, or social harm) than was previously known or recognized.

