- g) Relevant in-hospital therapies other than home therapy continuation, prophylactic antibiotics, (specify drug and dosage)
- h) NPPV (yes/no; if yes dates of start/end, in case of switch to IMV and then re-initiation of NPPV, enter only the end date of the second NPPV session)
- i) IMV (yes/no; if yes dates of start/end)
- j) HFNC (yes/no)
- k) ECMO (yes/no; if yes specify date of ECMO start and end)
- l) Tracheostomy (yes/no; if yes specify date of tracheostomy)
- m) Pronation (yes/no)
- n) Adverse events related to study treatment (Anaphylaxis, Agitation, Psychosis, Insomnia, Hyperglycemia/diabetes of new onset, Other: specify)
- o) In-hospital complications (Bradycardia, Diarrhea, Increased liver enzymes, Hypotension, Hypokalemia, Superinfection – specify microorganism, Shock requiring vasopressors not induced by the study drug, Acute renal failure, Disseminated Intravascular Coagulation, Acute myocardial infarction, Stroke, Atrial fibrillation or other major arrhythmias, Cardiorespiratory arrest, Pulmonary embolism, Other: specify).
- p) Date of hospital discharge
- q) Date of death

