### Reporting Timeline for SAE/Safety/SUSAR Events:

1. Urgent Reporting: all problems involving local deaths, whether related or not to the study drug, should be reported immediately – within 24 hours after first knowledge by the local investigator.
2. Expedited Reporting: All other problems must be reported as soon as possible but not later than 7 calendar days after first knowledge by the local investigator.

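### Section 7.2 merges SAE and SUSAR into one definition that contradicts 7.1, and item n in section 4.6 records the listed steroid effects only when judged treatment-related in an open-label trial

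*Protocol*

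**What the plan says.** Section 7.1 takes the ICH definition of an adverse event, one "that does not necessarily have a causal relationship with this treatment". It defines an SAE by a list of seriousness criteria, with no condition on expectedness or relatedness. It then states: "All deaths and SAEs will be notified to the local PI and site research governance, along with the DSMB". It closes: "All deaths and adverse events will be recorded and reported in the final analysis". The site PI classifies each event for relationship to study drug and for expectedness.

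Section 7.2, whose title covers collecting, recording and reporting, opens with a narrower scope: "Any events that are unexpected (in terms of severity or frequency), that can reasonably be attributed to the drug under study". Its definition reads: "SAE/Safety/SUSAR events refers to problems, in general, to include any incident, experience, or outcome (including adverse events) that meets ALL of the following criteria". The three criteria are that the problem is unexpected in nature, severity or frequency; that it is related or possibly related to taking part; and that it suggests a greater risk of harm than was known. The reporting timeline carries the same SAE/Safety/SUSAR label, yet says that "all problems involving local deaths, whether related or not to the study drug, should be reported immediately", within 24 hours. All other problems have 7 calendar days.

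The data list in section 4.6 has two safety items. Item n is headed "Adverse events related to study treatment" and lists anaphylaxis, agitation, psychosis, insomnia, hyperglycemia or new-onset diabetes, and an open entry. Item o lists in-hospital complications, among them raised liver enzymes, superinfection, acute renal failure, myocardial infarction, stroke, arrhythmia, pulmonary embolism and an open entry. It has no general relatedness condition; only its shock entry is limited to shock that the study drug did not cause.

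Section 5.1 says the trial is open label and that clinician and patient know the assigned arm.

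**The concern.** Two separate things go wrong.

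First, a site reading 7.1 and a site reading 7.2 would forward different sets of serious events under the same name. Section 7.1 itself names hyperglycemia, psychosis, raised liver enzymes and venous thrombosis among the possible serious effects of glucocorticoids, and does not anticipate that adverse events will be unexpected. Section 7.2 judges expectedness against the study documentation, which includes the protocol. By the protocol's own forecast, then, few SAEs would meet the 7.2 definition.

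Second, when an event enters the data only if someone who knows the arm attributes it to the drug, the recorded rate mixes how often the event happens with how readily it is blamed on that drug.

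This matters because section 3 names safety as an aim, and the arms differ in planned exposure. Under section 4.3 the methylprednisolone course lasts at least 8 days at full dose plus a taper of 3 + 3 + 2 + 2 + 2 + 2 = 14 days, so at least 22 days in all. The dexamethasone course lasts at most 10. Known steroid effects are the natural safety contrast between two such regimens. They are also the events that 7.2 tends to exclude as expected and that item n makes conditional on judgement.

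**Working it through.** The documents give no safety rate or safety sample size, so there is no figure to reproduce. The check sets the texts side by side.

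**Step 1: SAE under 7.1 against 7.2.**

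| Event | Notifiable under 7.1 | Inside the 7.2 definition | Deadline in 7.2 |
|---|---|---|---|
| Death, unrelated | Yes | No (fails relatedness) | 24 hours, by the timeline's own clause |
| Non-fatal SAE, unrelated | Yes | No (fails relatedness) | None |
| Non-fatal SAE, related, expected in nature, severity and frequency | Yes | No (fails unexpectedness) | None |
| Non-fatal SAE, related, known in nature but unexpected in severity or frequency | Yes | Yes, if it also suggests greater risk than known | 7 days |
| Non-fatal SAE, related, new in nature | Yes | Yes, if it also suggests greater risk than known | 7 days |

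Rows 2 and 3 are the conflict: SAEs under 7.1 that do not count under 7.2 and have no deadline in either section. Row 1 is a conflict inside 7.2: its timeline covers unrelated deaths, which its definition excludes.

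**Step 2: where the named steroid effects are recorded.** None of the five events listed in item n appears by name in item o. A psychosis or a new hyperglycemia judged unrelated, for instance put down to the infection, therefore has no designated field, although it could be typed into item o's open entry. Section 7.1 also counts laboratory changes that require therapy as adverse events, with no causality test. Treated hyperglycemia must thus be recorded under 7.1 whatever its cause, while item n asks for it only when attributed. Raised liver enzymes and pulmonary embolism are in item o and are not filtered.

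**Step 3: how attribution enters a recorded rate.** Let *p* be the true rate, equal in both arms, and *a* the share attributed to study drug. If only attributed events are entered:

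recorded difference = *p* × (*a*_MP − *a*_DM).

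The inputs below are assumptions chosen to show the mechanism; none comes from the protocol. Take *p* = 20%.

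- *a*_MP = 80%, *a*_DM = 50%: 0.20 × 0.80 = 16% against 0.20 × 0.50 = 10%, an apparent excess of 6 points on methylprednisolone.
- Equal attribution: difference 0.
- Attribution reversed, 50% and 80%: 10% against 16%, an apparent deficit of 6 points.

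So with no true difference, these assumptions give anything from −6 to +6 points. The sign depends only on which arm's events are attributed more readily.

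**The case against.** The best defence is that 7.1 already provides the safeguards. It sends all SAEs to the DSMB without a filter and requires all adverse events in the final analysis. Section 7.3 has the trial statisticians give the DSMB safety outcomes at each scheduled interim analysis. On this view the three criteria in 7.2 only mark which problems fall under the fast timelines, on top of the general duty. That reading is possible, but the text does not say so: the title of 7.2 covers collecting and recording, and its definition is labelled as covering SAEs. The defence shows what was probably intended and leaves the contradiction in place.

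Three stronger inferences are tempting and are not supported.

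- *That the data form records only related adverse events.* Item o is broad, has an open entry and carries no general relatedness test.
- *That known serious effects can never be reported.* They can qualify under 7.2 if unexpected in severity or frequency, and 7.1 requires notification in any case.
- *That the DSMB's comparison is shown to be incomplete, or the final safety comparison biased.* This would need 7.2 to override 7.1 and 7.3, which the protocol does not state.

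It is also fair to say that the site PI assesses relatedness against the product-characteristics listings, which limits free attribution by arm without removing it. No safety endpoint appears among the objectives in 2.2 or the outcomes in 4.5, and the primary outcome, 28-day survival, does not depend on attribution.

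**Conclusion.** Two limited points stand. Section 7.2 contradicts 7.1 on what an SAE is and which SAEs are reported, and its timeline contradicts its own definition on deaths; these texts must be reconciled. Item n makes recording of five listed steroid effects depend on attribution in an open-label trial, against 7.1's promise to record all adverse events. Arm comparisons of those effects are therefore exposed to ascertainment bias.

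The bias is a risk, not a demonstrated result. Its size and direction cannot be derived from the protocol, and the range of −6 to +6 points rests wholly on assumed rates. It would arise only if sites follow item n as worded and attribution differs between arms. The filter reaches item n and the shock entry of item o, not safety capture as a whole, and the efficacy conclusion is untouched. Correction is still worthwhile because no later analysis can recover events that were never entered.

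**What to change.** 1. In 7.2, give two definitions. An SAE is any event meeting the seriousness list in 7.1, notified to the DSMB regardless of expectedness or relatedness, as 7.1 already provides. A SUSAR is an event that is serious, unexpected and related. State which deadline applies to each.
2. In item n of section 4.6, remove the relatedness condition from the label, record every listed event with its date, and hold attribution in a separate field. Treat the shock entry of item o in the same way.
3. Compare item n events by arm regardless of attribution; an analysis restricted to attributed events can be shown beside it.

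The cost is wording in 7.2, relabelling item n and the shock entry with added date and attribution fields, and somewhat more events for sites to enter and forward. Sample size and the primary analysis do not change.

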### Reporting Timeline for SAE/Safety/SUSAR Events:

1. Urgent Reporting: all problems involving local deaths, whether related or not to the study drug, should be reported immediately – within 24 hours after first knowledge by the local investigator.
2. Expedited Reporting: All other problems must be reported as soon as possible but not later than 7 calendar days after first knowledge by the local investigator.

## 7.3. Safety Monitoring Plan

A DSMB will be established, comprising four independent physicians with statistical support provided to them by the Institute for Infectious Diseases “L. Spallanzani”. The trial statisticians will provide details of safety outcomes and any significant differences in primary outcomes according to treatment arm to the DSMB at any scheduled interim analysis. The stopping rule will be a statistically significant difference in primary outcomes between the two arms. The interim analysis results will be communicated to the trial team along with the DSMB recommendations for action. If there is a significant safety concern will be raised, the DSMB may recommend to the Principal Investigator that the trial should be stopped.

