## 3. Study design

This study is a phase 3 adaptive randomized controlled trial (2 parallel arms, allocation ratio 1:1) implemented during a massive epidemic emergency. Adaptation is a carefully considered

investigational procedure for modifying study parameters while the trial is ongoing, based on a review of the interim data analyses.(10–12)

Our adaptive trial is a sequential random controlled trial, with 2 interim analyses (K=3). We aim to evaluate the safety and efficacy of two different protocol of steroids therapy in adult patients with severe COVID-19.

The trial adaptive framework includes:

- a) a 3-stage sequential O'Brien and Fleming design;
- b) sample size re-calculation at each stage;
- c) binding stopping rule for efficacy according with preplanned critical values;
- d) binding stopping rule for futility according with a preplanned critical values.

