### 3.1. Sequential design

Sequential design is a pivotal element of the adaptive strategy that allows for assessing participants data while the trial is ongoing for optimizing trial performance. In this study, we include a 3-stage procedure with two homogeneous interim analyses and one final analysis (K=3). Sequential design is always associated with inflation of statistical error due to multiple comparisons on the same accrued set of data. To control for this bias, we have defined ad hoc statistical plan and define adequate error spending function. When the sample size expected for each interim analysis is reached, patients will continue to be enrolled and randomized until either the results of that interim analysis will be available or the minimum sample size expected for the subsequent stage will be reached.

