## 6.2. Sample size

Minimum and maximum sample size will significantly change according to the observed effect within the trial sample (expected **average** sample size is between 200 and 680 participants, figure 2). In particular, we expect to enroll 100 participants per arm at the first stage and then between 15 and 175 per arm for each eventual stage if the stopping rules were not met. The actual number of new participants in each arm will be calculated according to the maximum likelihood estimates on observed efficacy at each interim analysis with an overall conditional power for next stage equal to 90%. This approach allows either to minimize the number of enrolled participants if the experimental hypothesis is too conservative or to have a good power level if the experimental hypothesis is too optimistic. The average sample size with relative power and the overall probability for meeting stopping rules according to different level of efficacy of arm 1 vs. arm 2 are reported in figure 2 and figure 3, respectively.

	$H_0: \pi_T - \pi_C = 0$			
Critical values	Stage 1	Stage 2	Stage 3	
Reject H0 (Efficacy)	3.421	2.419	1.975	1.975
Accept H0 (Futility)	-0.695	1.002	1.975	1.975
Information rate	0.333	0.667	1	1
alpha spent	0.0003	0.0079	0.025	0.025

*Table 1 Preplanned critical values (Fisher test) for application of early stopping rules*

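### Section 7.3 sends the DSMB the 28-day survival comparison only when it is significant; it should go at every interim, and the stopping sentence should match Table 1

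*Protocol*

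**What the plan says.** Section 7.3 (Safety Monitoring Plan) names two things the DSMB gets at an interim. The first has no condition attached: "The trial statisticians will provide details of safety outcomes". The second does: "any significant differences in primary outcomes according to treatment arm to the DSMB at any scheduled interim analysis". The section then gives a single stopping criterion: "The stopping rule will be a statistically significant difference in primary outcomes between the two arms". It states no level or side, and it mentions neither Table 1 nor the futility rule.

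Other parts of the protocol bear on this:

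- Section 4.5 makes the proportion surviving at 28 days the primary outcome.
- Section 6.3 has the interim analyses produce the risk difference with 95% CI and the stopping criteria, with no significance condition. It does not say who receives them.
- Section 7.1: "All deaths and SAEs will be notified to the local PI and site research governance, along with the DSMB". Fatal events are SAEs by definition.
- Sections 3 and 6.2 (Table 1, and the Figure 1 caption) set one-sided efficacy bounds of 3.421, 2.419 and 1.975 and binding futility bounds of -0.695 and 1.002.
- Section 6.2 on the first look: "we expect to enroll 100 participants per arm at the first stage". The Figure 2 legend agrees: "first analysis is carried out at 200 patients".

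**The concern.** The primary outcome is survival, so the item that 7.3 filters by significance is also the most important safety comparison. At a first look with 100 per arm, significance is a weak filter: a mortality difference large enough to affect a benefit-risk judgement will often miss it. A DSMB working to the letter of 7.3 would hold individual death notices and safety details, but not the survival estimate by arm with its interval. The decision on what counts as noteworthy would have been made by the trial statisticians before the independent body saw the data.

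The stopping sentence adds to this. Without a level, a side or a reference to Table 1, it can be read as nominal two-sided 5%, as the Table 1 efficacy bound, or as the one-sided superiority test. These give very different answers for the same data, and none of them is the futility rule that sections 3 and 6.2 call binding.

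**Working it through.** **Plan's own figure.** The three-stage normal statistic was integrated numerically at information 1/3, 2/3 and 1, with efficacy bounds 3.421/2.419/1.975 and binding futility bounds -0.695/1.002. Cumulative one-sided alpha is 0.00031, 0.0079 and 0.0250, which reproduces Table 1 (0.0003, 0.0079, 0.025). The O'Brien-Fleming shape also checks: 1.975×√3 = 3.421 and 1.975×√1.5 = 2.419.

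**Inputs.** 100 per arm at the first look (section 6.2); DM survival 77%, so 23% deaths, and hypothesised MP survival 87% (section 6.1); Fisher's exact test (section 6.1). The protocol gives no harm scenario, so MP mortality of 33%, 30% and 28% are assumptions.

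**Method.** Exact enumeration of two independent binomials: P(event) = ΣΣ b(x;100,p_MP)·b(y;100,p_DM)·1[event at (x,y)], where x and y are survivors. Pooled Z = (x−y)/100 ÷ √(2p̄(1−p̄)/100), with p̄ = (x+y)/200. Significance is taken as nominal two-sided 5%, the most generous reading of 7.3.

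**Observed results with 23 DM deaths.**

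- 33 MP deaths: Fisher p = 0.156. Here p̄ = (67+77)/200 = 0.72 and Z = −0.10/√(2×0.72×0.28/100) = −1.57.
- 36 MP deaths: p = 0.062. 37 MP deaths: p = 0.044. The excess must reach 14 deaths to count as significant.
- Futility needs far less. At 28 MP deaths p̄ = 0.745 and Z = −0.05/√(2×0.745×0.255/100) = −0.81, already below −0.695.

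**Probabilities at the first look.**

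| True deaths, MP v DM | Two-sided Fisher p<0.05 | Pooled Z beyond ±1.96 | Futility crossed (pooled Z) | Neither futile nor Fisher-significant |
|---|---|---|---|---|
| 33% v 23% | 0.295 | 0.351 | 0.809 | 0.191 |
| 30% v 23% | 0.159 | 0.200 | 0.658 | 0.341 |
| 28% v 23% | 0.096 | 0.126 | 0.536 | 0.462 |
| 13% v 23% | 0.387 | 0.461 | 0.006 | 0.607 |

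The last row is the protocol's own hypothesis, with the excess deaths on DM: 1 − 0.387 − 0.006 = 0.607. If futility is also judged on the Fisher scale, the first row becomes 0.849 crossed and 0.151 neither, and the last row 0.010 and 0.603. With pooled Z for both, the last row is 1 − 0.461 − 0.006 = 0.533.

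**Other readings of significance, at 33% v 23%.** A mirrored 3.421 bound is reached with probability 0.022 (Fisher) or 0.031 (pooled Z). The one-sided test for MP superiority is essentially never significant when MP is worse.

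**The case against.** The strongest reply is that the wording is loose and the plan as a whole does not hide mortality.

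1. Deaths are not filtered. Every death and SAE goes to the DSMB, and the safety details in 7.3 carry no significance condition. The words about treatment arm can be read as covering both items, and the DSMB has statistical support. This stands. What remains is that section 7.1 describes notification of events and promises no denominators, rates by arm or interval, while 7.3 treats primary outcomes as a separate, filtered item.
2. Binding futility ends most trials in which MP is harmful. This also stands: about 81% at 33% v 23%, and observed results such as 33 v 23 or 36 v 23 deaths would both cross the bound. The cover weakens with smaller harms, is absent when the excess is on DM, and is not mentioned in 7.3. Nothing says that the DSMB receives the estimate when futility is met.
3. Section 6.3 produces the estimate at every interim, and 7.3 has interim results reach the trial team together with the DSMB's recommendations, which fits poorly with a DSMB that has not seen them. This supports loose drafting as the explanation. It also means that the two sections need reconciling, and that the correction is cheap.

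A reader might infer from the 0.29 that a 10-point excess of deaths would usually be concealed from the DSMB. The documents do not support that: the 0.29 concerns the formal survival comparison only, and points 1 and 2 limit its consequence. A reader might also infer that enrolment must run on substantially past the first look. Section 3.1 sets a ceiling instead: "patients will continue to be enrolled and randomized until either the results of that interim analysis will be available", or until the minimum for the next stage is reached. With the 15 per arm of section 6.2, that is at most 200 + 2×15 = 230.

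**Conclusion.** The point holds as a defect of stated wording. Followed literally, 7.3 withholds a non-significant 28-day survival comparison by arm from the DSMB, under a criterion with no level or side, although section 6.3 has already produced that comparison.

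At nominal two-sided 5% and 100 per arm, an assumed 33% v 23% mortality would fail the filter in about 65% (pooled Z) to 71% (Fisher) of first looks. The practical gap is narrower. About 19% of those trials would be neither stopped for futility nor significant, rising to about 34% at 30% v 23% and 46% at 28% v 23%. With the excess on DM at the hypothesised effect, about 61% of first looks are neither (53% if significance is also judged by pooled Z).

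These figures rest on the assumed harm rates, exactly 100 evaluable patients per arm, and the two-sided 5% reading. The DSMB remains informed of deaths throughout. The absence of earlier safety-only reviews is not an error in this document; their timing is usually a DSMB charter matter.

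**What to change.** Reword section 7.3 along these lines: *At every scheduled interim analysis the DSMB receives 28-day survival by arm with the risk difference and 95% CI described in section 6.3, and deaths and SAEs by arm with denominators, whether or not any difference is statistically significant.*

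Replace the sentence on the stopping rule with a reference to the efficacy and binding futility bounds of sections 3 and 6.2 (Table 1), so that 7.3 no longer carries a separate, undefined criterion.

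The cost is a short protocol amendment or matching charter text, and one table per interim built from analyses and notifications already planned. Critical values, alpha spending and sample-size rules are unchanged, and no extra looks are needed.
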